# 13.1.1 Analysis Sets

All efficacy analyses will be performed on the full analysis set (FAS), which will be defined as all randomized subjects who receive at least 1 dose of study drug and have post-baseline (post Day-1) data for the appropriate efficacy variable. The safety analysis set will include all randomized subjects who receive at least one dose of study drug.

# 13.1.2 Analysis of Demographics and Other Baseline Characteristics

Demographic and baseline variables will be summarized using the safety analysis set and analyzed to assess the comparability of the treatment groups provided by randomization. Summary statistics (N, mean, median, SD, and range) will be generated for continuous variables (eg, age and weight). The numbers and percentages of subjects will be presented for categorical variables (eg, gender, race).

## **13.1.3 Efficacy Analysis**

The primary efficacy variable will be the percentage of days without daytime or night time heartburn over 4 weeks as assessed by daily eDiary. Comparisons between dexlansoprazole capsules and placebo will be made using a Wilcoxon rank-sum test.

The secondary efficacy variable will be the percentage of days without nighttime heartburn over 4 weeks as assessed by daily eDiary. Comparisons between dexlansoprazole capsules and placebo will be made using a Wilcoxon rank-sum test.

An additional efficacy variable will be the severity of GERD symptoms at Weeks 2 and 4 as assessed by the investigator. The severity of GERD symptoms at Weeks 2 and 4 will be analyzed using a Cochran-Mantel-Haenszel (CMH) test for ordered responses with baseline severity as the stratum. The percentage of days without rescue medication over 4 weeks as assessed by daily eDiary will be analyzed using Wilcoxon rank-sum test.

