## 7.1 Inclusion Criteria

Subject eligibility is determined according to the following criteria:

- 1. In the opinion of the investigator, the subject is capable of understanding and complying with protocol requirements.
- 2. The subject or, when applicable, the subject's legally acceptable representative signs and dates a written, informed consent form and any required privacy authorization prior to the initiation of any study procedures.
- 3. The subject is a man or woman and aged at least 18 years.
- 4. Subjects identifying their main symptom as a burning feeling in the mid epigastric area and/or chest area (ie, heartburn).
- 5. The subject must have a history of symptomatic GERD for 6 months or longer prior to Screening with GERD symptoms that were responsive to acid-suppressive therapy.
- 6. The subject must have episodes of heartburn for any 4 or more days during the 7 days prior to Day -1 as recorded in the eDiary.
- 7. All women subjects of child bearing potential who are sexually active agree to routinely use adequate contraception from signing of the informed consent throughout the duration of the study and for 30 days after the last dose of study medication.
- 8. All men subjects who are nonsterilized\* and sexually active with women partner of childbearing potential\* agree to use adequate contraception\* from signing of informed consent throughout the duration of the study and for 30 days after the last dose of study medication.

\*Definitions and acceptable methods of contraception are defined in Section 9.1.11 Contraception and Pregnancy Avoidance Procedure and reporting responsibilities are defined in Section 9.1.12 Pregnancy.

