# 9.1.7 Daily eDiary

Subjects will be given an eDiary on the first day of the Screening Period. Throughout the Screening Period and Treatment Period, subjects will document the presence and maximum severity of daytime and nighttime heartburn symptoms each day in their daily eDiary. Subjects will also record the use of rescue medication. If the subject experiences no heartburn on any given day, they should also provide this information. The daily eDiary should be completed every morning upon waking and every evening before bedtime. The last entry for the Treatment Period is in the morning prior to their Week 4/Final Visit site visit.

The electronic diaries will be reviewed at subsequent visits. Subjects must bring their electronic dairy device at every visit. The severity of heartburn will be graded by the subject according to the definitions outlined in Appendix F. Should the electronic diaries be lost or destroyed, the subject should contact the site immediately to receive additional eDiary to insure continuity of symptom reporting.

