# **13.0 STATISTICAL METHODS**

# 13.1 Statistical and Analytical Plans

A statistical analysis plan (SAP) will be prepared and finalized prior to unblinding of subject's treatment assignment. This document will provide further details regarding the definition of analysis variables and analysis methodology to address all study objectives.

A blinded data review will be conducted prior to unblinding of subject's treatment assignment. This review will assess the accuracy and completeness of the study database, subject evaluability, and appropriateness of the planned statistical methods.

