## **13.3** Determination of Sample Size

A total of 200 subjects are planned to be enrolled into this study to ensure 160 subjects with symptomatic nonerosive GERD will complete the study (assuming a 20% dropout rate). The sample size of 80 subjects per treatment group will provide at least 95% power at the 0.05 two-sided significance level to detect a difference of 25% in the mean percentage of days without daytime or nighttime heartburn over 4 weeks between dexlansoprazole capsules (50%) and placebo (25%). The dexlansoprazole and placebo rates were estimated from prior dexlansoprazole study T-GD05-137. The common standard deviation was assumed to be 35%.

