5.6 Demographic and Other Baseline Characteristics

Demographic and baseline characteristics variables were summarized using the safety analysis set.

For continuous variables (age, weight, height, and body mass index [BMI]), summary statistics were generated.

For categorical variables, the number and percentage of subjects in each category was presented.

The following baseline characteristics were summarized.

- Number of days with daytime or nighttime heartburn between Study Days -8 and -2, inclusive.
- Number of days with nighttime heartburn between Study Days -8 and -2, inclusive.
- Number of days with daytime heartburn between Study Days -8 and -2, inclusive.
- Mean severity of daytime and nighttime heartburn between Study Days -8 and -2, inclusive.
- Mean severity of nighttime heartburn between Study Days -8 and -2, inclusive.
- Mean severity of daytime heartburn between Study Days -8 and -2, inclusive.
- Baseline severity of GERD symptoms as assessed by the investigator.
- Baseline number of days with daytime/nighttime rescue medication use.

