5.10.1 Primary Efficacy Endpoint

The percentage of days with neither daytime nor nighttime heartburn over the 4 weeks of treatment was summarized descriptively. Comparisons between dexlansoprazole capsules and placebo was made using a Wilcoxon rank-sum test. The two-sided p-value was presented for the difference between dexlansoprazole capsules and placebo; the difference was considered statistically significant if the p-value was less than 0.05.

The percentage of days with neither daytime nor nighttime heartburn was calculated for each subject who has at least 1 daytime or nighttime heartburn result (presence or absence of heartburn) during the 4 weeks of treatment (up to last dose day or Day 35 whichever is first) by calculating:

$$\text{Percentage of days with neither daytime nor nighttime heartburn} = \frac{\text{(the days that were heartburn-free during Treatment Period)}}{\text{(Total number of days for which either a daytime or nighttime result was marked during Treatment Period)}} \times 100\%;$$

all entries on a day must be heartburn-free in order for the day to be counted as a day with neither daytime nor nighttime heartburn.

The days with missing diary results for both daytime and nighttime were excluded from the numerator and denominator. If a subject prematurely terminated, the Treatment Period was defined as from first dose date to last dose date + 1 day. If last dose date was missing, then 35 days was imputed as treatment period.

Subgroup Analyses:

Similar descriptive statistics and Wilcoxon rank-sum tests were repeated on the primary endpoint to evaluate the treatment effect within the different baseline subpopulation levels as follows:

- Age (<45, ≥45 to <65, ≥65 years).
- Gender (male, female).
- BMI (<25, 25-<30, ≥30 kg/m²).
- *H pylori* status (positive, negative).
- Overall study drug compliance (<80%, 80-<90%, ≥90%).

Ad Hoc Sensitivity Analysis

Similar descriptive statistics and two sample T-test were repeated on the primary endpoint to evaluate the treatment effect.

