5.10.2 Secondary Efficacy Endpoints

Descriptive statistics (mean, median, standard deviation, minimum and maximum) were presented similarly to the primary endpoint. Comparisons between dexlansoprazole capsules and placebo was made using a Wilcoxon rank-sum test. The p-value was presented for the difference between dexlansoprazole capsules and placebo; the difference was considered significant if the two-sided p-value was less than 0.05. The ad hoc sensitivity analysis described for the primary endpoint was also performed on the secondary endpoint.

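### The rank-sum tests for the diary endpoints are valid, but a pre-specified one-covariate rank ANCOVA on baseline diary heartburn would be a small, low-cost gain: under 1 point of power at the planned effect, more only if the effect is smaller

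*Protocol*

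**What the plan says.** Protocol 13.1.3 gives the same sentence for the primary endpoint (percentage of days with neither daytime nor nighttime heartburn) and the secondary endpoint (percentage of days without nighttime heartburn): "Comparisons between dexlansoprazole capsules and placebo will be made using a Wilcoxon rank-sum test". SAP 5.10.1 repeats it in the past tense: "Comparisons between dexlansoprazole capsules and placebo was made using a Wilcoxon rank-sum test". SAP 5.10.2 uses the same test for the secondary endpoint, where "the difference was considered significant if the two-sided p-value was less than 0.05". No covariate or stratum is named for either.

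The diary that yields these endpoints also runs before treatment. Protocol 9.1.7: "Throughout the Screening Period and Treatment Period, subjects will document the presence and maximum severity of daytime and nighttime heartburn symptoms each day". SAP 5.6 derives baseline summaries from it, beginning with "Number of days with daytime or nighttime heartburn between Study Days -8 and -2, inclusive", and also nighttime days and mean severities. These appear only among the descriptive baseline characteristics. By contrast, Protocol 13.1.3 and SAP 5.10.3 stratify the investigator-rated symptom severity test by its own baseline.

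Power is given only for the primary endpoint (Protocol 13.3): at least 95% with 80 subjects per arm for means of 50% and 25%. On variability the section says: "The common standard deviation was assumed to be 35" percent.

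**The concern.** A baseline measurement on nearly the same scale as the outcome is often associated with it. Where it is, adjusting a randomized comparison for it reduces unexplained variation, and power rises with no extra subjects and no change in the type I error rate. The plan collects such a measurement, derives it, and adjusts for baseline on a lesser endpoint, but leaves it out of the tests of the two main diary endpoints. Only efficiency is at stake. The question is whether the gain is large enough to be worth pre-specifying.

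**Working it through.** **Inputs.** Protocol 13.3: means 50 and 25, SD 35, 80 per arm, two-sided 0.05, 20% dropout. SAP Table 7.a: placebo 36.98 (SD 31.999, n=108), dexlansoprazole 47.21 (SD 35.995, n=107). Assumed, because neither document gives them: the within-arm correlation r between baseline and outcome, a 15-point effect as a middle case, and the spread of baseline days.

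**Step 1: the plan's own figure.** The standardized difference is 25/(35 × √(2/80)) = 25/5.534 = 4.518. Power is Φ(4.518 − 1.960) = 99.5% (99.4% by noncentral t). Scaling n by the relative efficiency of the rank-sum test gives 99.3% at 0.955 and 98.7% at the lower bound of 0.864. Enrolment: 160/0.80 = 200. The stated minimum of 95% is met for the primary endpoint.

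**Step 2: gain from one covariate.** Replace SD by SD × √(1 − r²), that is, multiply by 0.980 at r=0.2 and 0.954 at r=0.3. The pooled SD of the reported data is √[(107 × 31.999² + 106 × 35.995²)/213] = 34.05, and the reported difference is 47.21 − 36.98 = 10.23.

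| Scenario | Unadjusted power | Gain, r=0.2 | Gain, r=0.3 |
|---|---|---|---|
| Planned: 25 points, 80 per arm, efficiency 0.955 | 99.3% | +0.16 | +0.32 |
| Planned, efficiency 0.864 | 98.7% | +0.26 | +0.53 |
| Assumed 15 points, SD 35, 108 and 107, t-test | 87.9% | +1.2 (89.1%) | +2.7 (90.6%) |
| Reported 10.23 points, about 107.5 per arm, efficiency 0.955 | 57.6% | +1.7 | +4.0 |

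**Step 3: simulation of rank-sum against one-covariate rank ANCOVA.** The outcome is a beta-binomial percentage over 28 days, with baseline days limited to 4 to 7 (assumed shares 0.2, 0.2, 0.2, 0.4).
- Planned inputs: both tests reach about 99.9%, and the gain is at most 0.1 point.
- 25 versus 40, SD 35, 108 and 107 subjects: the rank-sum test has 98.0 to 98.4%, and the gain is at most about 1.0 point for r up to about 0.4.
- Reported means and SDs: 52.9% to 54.3% at r=0.19 (+1.4) and 53.5% to 56.5% at r=0.29 (+3.0). An independent repeat gave +1.5 and +3.7. A variant with a common SD of 0.34 (34 points) gave +2.6 at r≈0.21 and +4.8 at r≈0.31, so the size also depends on the assumed distribution. At r=0.40 the gain was +6.7.
- Type I error for r from 0 to 0.39: rank-sum 4.6 to 5.1%, rank ANCOVA 4.8 to 5.0%.

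**Step 4: what it could cost.** With r=0 at the reported effect, power moves from 53.1% to 52.9%, a loss of 0.2; allow up to about 0.5. If 30% of subjects had only 4 to 6 recorded screening days and 5% had none (assumptions), the +1.4 and +3.0 above fall to +0.8 and +2.1.

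All of these figures concern the primary endpoint.

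**The case against.** The strongest reply is that there is no defect here. An unadjusted rank test is an ordinary choice for a bounded, skewed percentage. It holds its level, and at the planned effect there is almost no power left to gain. The larger gains arise only at effects well below the plan's, including one learned after unblinding. They also rest on an r that no document reports. Entry required "episodes of heartburn for any 4 or more days during the 7 days prior to Day -1", which narrows the range of baseline days and makes low values of r more plausible. The remedy needs a new derived variable and an exception to SAP 5.2.2, which imputes no missing values other than dates. The SAP supplied is a report written after unblinding, so nothing can be pre-specified in it.

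Most of this stands, and it limits the point to an optional improvement. It is not known that the baseline diary is prognostic here. Nor are the screening diary data idle: they decide eligibility and describe group comparability, and are absent only from the two tests. The restricted-range argument is weaker for nighttime heartburn, because the entry rule counts any heartburn.

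The objection does not defeat the suggestion. The possible loss is about half a point or less, the data already exist, and the plan itself adjusts for baseline on another endpoint.

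**Conclusion.** The point holds as a low-priority efficiency suggestion. The rank-sum tests are valid and the primary comparison has about 99% power at its planned inputs. If r is 0.2 to 0.3, a one-covariate rank ANCOVA would add under 1 point at 25 points. For an assumed 15-point effect it would add about 1 to 3 points by the t-test approximation, or 1 point or less where the rank-sum test is already at 98%. At the effect reported after unblinding it would add about 1.5 to 4 points, a figure that illustrates size and shows no fault in the plan. A larger r would give more, and r near zero would give nothing.

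Three stronger readings are not supported:
- A reader might infer that leaving out the covariate biased the comparison. Randomization protects the unadjusted test, and SAP 6.4 reports similar baseline heartburn means in the two groups.
- A reader might infer that adjustment would have turned p=0.057 into a significant result. The documents give neither r nor subject-level data, and the adjusted estimate could move either way.
- A reader might take the power statement to cover both diary endpoints. Protocol 13.3 states none for the nighttime endpoint, and no gain is quantified for it here.

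**What to change.** Make the change in Protocol 13.1.3 and in the analysis plan that, under Protocol 13.1, "will be prepared and finalized prior to unblinding of subject's treatment assignment":
- Name one primary test: rank ANCOVA with a single covariate, the proportion of recorded diary days with heartburn over Days -8 to -2. Use the nighttime version for the secondary endpoint.
- Keep the unadjusted Wilcoxon rank-sum test as a supportive analysis.
- Keep every FAS subject. Use whatever screening days were recorded; if there are none, assign the baseline median pooled across arms, stated as an exception to SAP 5.2.2.

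The cost is one derived variable (SAP 5.6 has the count of days, not the proportion of recorded days), one model and one missing-baseline rule. There is no new data collection and no extra subjects. Up to about 0.5 points of power is lost if baseline is not prognostic, and the gain shrinks where screening diaries are short.

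For the existing unblinded report, an adjusted analysis could be added only as a labelled post-hoc result, with the p=0.057 conclusion left as it is.

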## 13.1.4 Safety Analysis

Safety will be assessed by summarizing the incidence of AEs, clinical laboratory tests, gastrin levels, ECG and vital signs using the safety analysis set.

Dexlansoprazole Capsules	
Study No. TAK-390MR_302	Page 61 of 82
Protocol Incorporating Amendment No. 03	20 February 2017

All AEs will be coded using MedDRA. Treatment-emergent adverse events (TEAE) will be summarized using preferred term and primary system organ class overall, by severity, and by relationship to study drug for each treatment group. Separate summaries will also be generated for treatment-related adverse events (TRAEs) overall and by severity. Adverse events that were reported more than once by a subject during the treatment period will be counted only once for that subject at the maximum severity.

Other safety assessments (ECG results, clinical laboratory values, gastrin levels, physical exams and vital signs) will be summarized by treatment group at all visits assessed using descriptive statistics. Values outside the reference ranges and markedly abnormal laboratory values will be flagged and tabulated.

# 13.2 Interim Analysis and Criteria for Early Termination

No interim analysis is planned.

## **13.3** Determination of Sample Size

A total of 200 subjects are planned to be enrolled into this study to ensure 160 subjects with symptomatic nonerosive GERD will complete the study (assuming a 20% dropout rate). The sample size of 80 subjects per treatment group will provide at least 95% power at the 0.05 two-sided significance level to detect a difference of 25% in the mean percentage of days without daytime or nighttime heartburn over 4 weeks between dexlansoprazole capsules (50%) and placebo (25%). The dexlansoprazole and placebo rates were estimated from prior dexlansoprazole study T-GD05-137. The common standard deviation was assumed to be 35%.

# 14.0 QUALITY CONTROL AND QUALITY ASSURANCE

### 14.1 Study-Site Monitoring Visits

Monitoring visits to the study site will be made periodically during the study to ensure that all aspects of the protocol are followed. Source documents will be reviewed for verification of data recorded on the eCRFs. Source documents are defined as original documents, data, and records. The investigator and institution guarantee access to source documents by the sponsor or its designee (CRO) and by the IRB or IEC.

All aspects of the study and its documentation will be subject to review by the sponsor or designee (as long as blinding is not jeopardized), including but not limited to the Investigator's Binder, study medication, subject medical records, informed consent documentation, documentation of subject authorization to use personal health information (if separate from the informed consent forms), and review of eCRFs and associated source documents. It is important that the investigator and other study personnel are available during the monitoring visits and that sufficient time is devoted to the process.

#### 14.2 **Protocol Deviations**

The investigator should not deviate from the protocol, except where necessary to eliminate an immediate hazard to study subjects. Should other unexpected circumstances arise that will require deviation from protocol-specified procedures, the investigator should consult with the medical monitor (and IRB or IEC, as required) to determine the appropriate course of action. There will be no exemptions (a prospective approved deviation) from the inclusion or exclusion criteria.

The site should document all protocol deviations in the subject's source documents. In the event of a significant deviation, the site should notify the sponsor or its designee (and IRB or EC, as required). Significant deviations include, but are not limited to, those that involve fraud or misconduct, increase the health risk to the subject, or confound interpretation of primary study assessment. The Significant Protocol Deviation eCRF is to be completed for deviations that are identified as significant by the sponsor.

## 14.3 Quality Assurance Audits and Regulatory Agency Inspections

The study site also may be subject to quality assurance audits by the sponsor or designees. In this circumstance, the sponsor-designated auditor will contact the site in advance to arrange an auditing visit. The auditor may ask to visit the facilities where laboratory samples are collected, where the medication is stored and prepared, and any other facility used during the study. In addition, there is the possibility that this study may be inspected by regulatory agencies, including those of foreign governments (eg, the Food and Drug Administration [FDA], the United Kingdom Medicines and Healthcare products Regulatory Agency [MHRA], the Pharmaceuticals and Medical Devices Agency of Japan [PMDA]). If the study site is contacted for an inspection by a regulatory body, the sponsor should be notified immediately. The investigator and institution guarantee access for quality assurance auditors to all study documents as described in Section 14.1.

# 15.0 ETHICAL ASPECTS OF THE STUDY

This study will be conducted with the highest respect for the individual participants (ie, subjects) according to the protocol, the ethical principles that have their origin in the Declaration of Helsinki, and the ICH Harmonised Tripartite Guideline for GCP. Each investigator will conduct the study according to applicable local or regional regulatory requirements and align his or her conduct in accordance with the "Responsibilities of the Investigator" that are listed in Appendix B. The principles of Helsinki are addressed through the protocol and through appendices containing requirements for informed consent and investigator responsibilities.

